4.2 Exclusion Criteria

Subjects fulfilling anv of the following criteria are not eligible for inclusion in this study. To ensure the recruitment of a representative sample of all eligible subjects, the investigator may apply no additional exclusions.

- On excluded therapies, not on a stable dose of a therapy, or incompletely washed out for a therapy (Table-1.)
- Known hypersensitivity or other adverse reaction to Baricitinib (LY3009104)
- Variants of LP deemed by the investigators to be inappropriate for Baricitinib (LY3009104) including but not limited to:
 - o Drug-induced LP
 - o Predominant non-cutaneous variants of LP, note that individuals can have disease in non-cutaneous areas; however, they must also have cutaneous disease.
 - Lichen Planopilaris
 - Oral Lichen planus
- Pregnant or nursing (lactating) women (pregnancy is defined as the state of a female after conception and until the termination of gestation, confirmed by a positive human chorionic gonadotropin (hCG) laboratory test)
- Women of childbearing potential [Post-menopausal or not of child-bearing potential is defined by 1 year of natural (spontaneous) amenorrhea or surgical bilateral oophorectomy (with or without hysterectomy), total hysterectomy or tubal ligation at least 6 weeks ago. Oophorectomy alone must be confirmed by follow up hormone level assessment to be considered not of child-bearing potential, defined as all women

physiologically capable of becoming pregnant, unless they are using basic methods of contraception which includes:

- o Total abstinence (Periodic abstinence and withdrawal are not acceptable methods of contraception)
- Female sterilization (bilateral oophorectomy with or without hysterectomy), total hysterectomy, or tubal ligation at least 6 weeks before taking study treatment. Oophorectomy alone requires follow up hormone level assessment for fertility.
- Male sterilization (at least 6 months prior to screening). The vasectomized male partner should be the sole partner for that subject.
- o Barrier methods of contraception: condom or occlusive cap.
- Use of oral, injected or implanted hormonal methods of contraception or other forms or hormonal contraception that have complete efficacy (failure <1%). (The dose of the contraceptive should be stable for 3 months)
- Active ongoing inflammatory diseases of the skin other than LP that might confound the evaluation of the benefit of Baricitinib (LY3009104)
- Underlying condition (including, but not limited to metabolic, hematologic, renal, hepatic, pulmonary, neurologic, endocrine, cardiac, infectious or gastrointestinal conditions) which, in the opinion of the investigator, significantly immunocompromises the subject and/or places the subject at unacceptable risk for receiving an immunomodulatory therapy
- Moderate-to-severe renal impairment including patients with estimated glomerular filtration rate (eGFR) <60 mL/min/1.73m²
- Active systemic infections during the 2 weeks prior to randomization (common cold viruses excluded) or any infection that reoccurs on a regular basis.
- Current severe progressive or uncontrolled disease which the investigator renders the subject unsuitable for the trial or puts the subject at increased risk
- Have had any major surgery within 8 weeks prior to screening or will require major surgery during the study that, in the opinion of the investigator would pose an unacceptable risk to the patient.
- Have experienced any of the following within 12 weeks of screening: VTE (DVT/pulmonary embolism [PE]), myocardial infarction (MI), unstable ischemic heart disease, stroke, or New York Heart Association Stage III/IV heart failure.
- Have a history of recurrent (≥ 2) VTE (DVT/PE).
- Have a history of lymphoproliferative disease; have signs or symptoms suggestive of possible lymphoproliferative disease, including lymphadenopathy or splenomegaly; have active primary or recurrent malignant disease; or have been in remission from clinically significant malignancy for <5 years prior to randomization.
- Have had symptomatic herpes zoster infection within 12 weeks prior to randomization.
- Have a history of disseminated/complicated herpes zoster (for example, ophthalmic zoster or CNS involvement).
- ALT or AST >2 x upper limits of normal (ULN); alkaline phosphatase (ALP) ≥2 x ULN; total bilirubin ≥1.5 x ULN; hemoglobin <10 g/dL (100.0 g/L); total white blood cell count <3000 cells/μL (<3.00 x 103/μL or <3.00 billion/L); neutropenia (absolute neutrophil count [ANC] <1500 cells/□L) (<1.50 x 103/□L or <1.50 billion/L); lymphopenia (lymphocyte count <1000 cells/μL) (<1.00 x 103/μL or <1.00 billion/L); thrombocytopenia (platelets <100,000 cells/μL) (<100 x 103/μL or <100 billion/L)
- Have a positive test for hepatitis B virus (HBV) defined as:
 - a. positive for hepatitis B surface antigen (HBsAg), or
 - b. positive for hepatitis B core antibody (HBcAb) and positive for hepatitis B virus deoxyribonucleic acid (HBV DNA)

Note: Patients who are HBcAb-positive and HBV DNA-negative may be enrolled in the study but will require additional HBV DNA monitoring during the study.

- Have hepatitis C virus (HCV) infection (hepatitis C antibody-positive and HCV ribonucleic acid [RNA]-positive).
 - Note: Patients who have documented anti-HCV treatment for a past HCV infection AND are HCV RNA-negative may be enrolled in the study.
- Have evidence of HIV infection and/or positive HIV antibodies.

- Have had household contact with a person with active TB and did not receive appropriate and documented prophylaxis for TB.
- Have evidence of active TB or latent TB
- Have evidence of active TB, defined in this study as the following:
 - o Positive purified protein derivative (PPD) test (≥5 mm induration between approximately 2 and 3 days after application, regardless of vaccination history), medical history, clinical features, and abnormal chest x-ray at screening.
 - QuantiFERON®-TB Gold test or T-SPOT®.TB test (as available and if compliant with local TB guidelines) may be used instead of the PPD test. Patients are excluded from the study if the test is not negative and there is clinical evidence of active TB.

Exception: patients with a history of active TB who have documented evidence of appropriate treatment, have no history of re-exposure since their treatment was completed, have no clinical features of active TB, and have a screening chest x-ray with no evidence of active TB may be enrolled if other entry criteria met. Such patients would not be required to undergo the protocol-specific TB testing for PPD, QuantiFERON®-TB Gold test, or T-SPOT®.TB test but must have a chest x-ray at screening (i.e., chest imaging performed within the past 6 months will not be accepted).

- Have evidence of untreated/inadequately or inappropriately treated latent TB, defined in this study as the following:
 - o Positive PPD test, no clinical features consistent with active TB, and a chest x-ray with no evidence of active TB at screening; or
 - o If the PPD test is positive and the patient has no medical history or chest x-ray findings consistent with active TB, the patient may have a QuantiFERON®-TB Gold test or T-SPOT®.TB test (as available and if compliant with local TB guidelines). If the test results are not negative, the patient will be considered to have latent TB (for purposes of this study); or
 - O QuantiFERON®-TB Gold test or T- SPOT®.TB test (as available and if compliant with local TB guidelines) may be used instead of the PPD test. If the test results are positive, the patient will be considered to have latent TB. If the test is not negative, the test may be repeated once within approximately 2 weeks of the initial value. If the repeat test results are again not negative, the patient will be considered to have latent TB (for purposes of this study).
- Have been exposed to a live vaccine within 12 weeks of randomization or are expected to need/receive a live vaccine during the course of the study (with the exception of herpes zoster vaccination).
- Have donated more than a single unit of blood within 4 weeks prior to screening or intend to donate blood during the course of the study.
- Have a history of intravenous drug abuse, other illicit drug abuse, or chronic alcohol abuse within the 2 years prior to screening or are concurrently using, or expected to use during the study, illicit drugs (including marijuana).

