There is an increased risk of infection with use of Baricitinib (LY3009104). This will be monitored for. Baricitinib (LY3009104) may increase the risk of infections and reactivation of latent infections such as Tuberculosis, Valley Fever or viral infections such as herpes zoster (shingles) or herpes simplex (cold sore). Please seek medical advice if signs or symptoms suggestive of infection occur.

Allergy:

It is possible that some people could have an allergic reaction to Baricitinib (LY3009104).

Venous thromboembolism:

Events of deep venous thrombosis (DVT) and pulmonary embolism (PE) have been reported in rare occurrences with patients taking Baricitinib (LY3009104). While we do not expect such events to occur, patients should seek medical advice if they experience signs or symptoms of DVT/PE such as significant shortness of breath, bloody cough or lower leg swelling, redness and pain.

Cancer Risk:

Baricitinib (LY3009104) may have the potential to affect the subject's immune system; they may be at increased risk for infections and possibly cancer. Live vaccines should not be given concurrently with Baricitinib (LY3009104).

Pregnancy Risk:

The effect of the study drug on a fetus (developing baby still in the womb), or on a breastfeeding infant, is unknown and may be harmful. Because of these risks, women cannot take part in this study if they are pregnant or breastfeeding.

Skin biopsy:

A skin biopsy is generally a safe procedure, but some potential risks may include local pain, mild local bruising, bleeding, scarring, and an infection at the site where the skin biopsy was performed. If a topical antibiotic is used afterwards, then there is a small risk of an allergic reaction.

Chest X-ray:

Subjects will be exposed to radiation from the chest x-ray. The amount of radiation has a low risk of harmful effects.

ECG:

There may be mild discomfort from the sticky pads and a possibility of the skin being irritated by the adhesive on the sticky pads. Chest hair may need to be shaved prior to the placement of the sticky pads.

Blood draw:

The risks of drawing blood include pain, bruising, lightheadedness, and/or fainting, or rarely, infection at the site of the needle stick.

Other:

As with all research, there is a chance that confidentiality could be compromised; however, we take precautions to minimize this risk.

2 Study Objectives

Primary Objective:

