3.2 Number of Subjects

12 subjects will be enrolled in this study.

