3.3 Duration of Participation

The study consists of 3 epochs: screening/washout period (at least 1 week and up to 4 weeks), treatment epoch (16 weeks from screen/washout), and follow up epoch (4 weeks). The screening and washout period will allow for treatment naïve/ new diagnosis LP to undergo evaluation and diagnosis and for treatment refractory to undergo a washout. The total duration of the study will be 21-24 weeks, with the option to enroll in a 3 month extension with a dose escalation to 4 mg for patients who demonstrate response to treatment, but have not yet achieved PGA 0

Tables:

Table-1: Prohibited treatment

Prohibited treatments ^{†,‡}	Washout period (before Randomization Visit)
Any concomitant oral or topical JAK inhibitor	Prohibited
Any biologic drug	Stable dose for 3 months
Immunomodulation treatments for LP§	4 weeks
[e.g., methotrexate, cyclosporine A, corticosteroids (oral, i.v.,	
intramuscular, s.c., intra-articular, transdermal),	
mycophenolate mofetil, azathioprine]	
Topical treatment that is likely to impact signs and symptoms of LP (e.g., pimecrolimus, tacrolimus)	2 weeks
Non-immunosuppressive agents (tetracycline antibiotics & niacinamide)	2 weeks
Prohibited regimen of Topical Corticosteroids (TCS)	
TCS on any location on body (including face, scalp and/or genitoanal area)	2 weeks

[†]If the prohibited treatment is being used during the study for any indication, the subject must discontinue use of the prohibited treatment if he/she wishes to continue in the study.

[‡] In case of undue safety risk for the subject, the subject should discontinue study treatment at the discretion of the investigator/qualified site staff. If the subject received a live virus vaccination during the study, the subject must discontinue study treatment.

§Inhalative CS with only a topical effect (e.g., to treat asthma) are not considered "systemic immunomodulation treatments" and are therefore acceptable as co-medication. Immunosuppressive medication for conditions other than LP will be allowed.

Table 2: Washout Periods for Monoclonal Antibodies (Biologic Drugs)

Brand	Generic Name	Recommended Minimum
Name		Washout (approximately 5 half-lives)
ACTEMRA	Tocilizumab	8 weeks
CIMZIA	Certolizumab pegol	10 weeks
COSENTYX	Secukinumab	16 weeks
DUPIXENT	Dupilumab	12 weeks
ENBREL	Etanercept	4 weeks
HUMIRA	Adalimumab	8 weeks
KEVZARA	Sarilumab	7 weeks
ORENCIA	Abatacept	8 weeks
REMICADE	Infliximab	6 weeks
RITUXIN	Rituximab	6 months
SIMPONI	Golumimab	10 weeks

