3.4 Primary Study Endpoints

Overall response by PGA of skin at week 16.

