4.4 Early Withdrawal of Subjects

4.4.1 When and How to Withdraw Subjects

- Subject safety issues
- Failure of subject to adhere to protocol requirements
- Disease progression
- Subject decision to withdraw from the study (withdrawal of consent)

Subjects who withdraw from the study for any reason will have their information recorded at the time of withdrawal. At the time of withdrawal, the subject will be considered at the final treatment date and will move into the treatment observation phase (4 weeks). Subjects will not be replaced. Follow up for subjects will continue to follow the normal follow up (Table-2)

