5.2 Treatment Regimen

Subjects will administer Baricitinib (LY3009104) 2 mg tablet once daily on an empty stomach. Treatment will take place from Day 0 to Week 16.

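### Section 4.2 drops the entry screen for a planned live zoster vaccine, while sections 1.6, 3.3 (Table 1) and 3.6 treat any live vaccine as incompatible with study drug

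*Combined protocol and SAP*

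**What the plan says.** The protocol addresses live vaccines in four places.

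- **Section 4.2 (entry).** One criterion has two parts: exposure to a live vaccine in the 12 weeks before entry, and patients who "are expected to need/receive a live vaccine during the course of the study (with the exception of herpes zoster vaccination"). The parenthesis closes the sentence.
- **Section 1.6 (risks).** "Live vaccines should not be given concurrently with Baricitinib (LY3009104"). No vaccine is exempted.
- **Section 3.3, Table 1 footnote.** "If the subject received a live virus vaccination during the study, the subject must discontinue study treatment". No vaccine is exempted.
- **Section 3.6.** The same stop rule is repeated in the same terms, again without an exemption.

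The opening of section 4.2 also tells the investigator not to add exclusions beyond those listed. The primary endpoint in section 3.4 is "Overall response by PGA of skin at week 16". On withdrawals, section 4.4.1 says "Subjects will not be replaced".

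**The concern.** The entry rule and the conduct rules point in different directions for one vaccine. An exception to a rule about live vaccines has work to do only for a live product, because a non-live vaccine was never excluded. On its plain wording, a patient who expects to receive a live zoster vaccine during the study is eligible. If that vaccine is then given on drug, it goes against section 1.6 and triggers the stop rule.

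The stop rule acts only after the patient has been exposed. The entry criterion and the advice in section 1.6 are the two safeguards that act beforehand, and section 4.2 takes one of them away for zoster.

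Zoster vaccination is a foreseeable question in this trial: section 1.4 lists herpes zoster among the adverse drug reactions in rheumatoid arthritis, and section 1.6 lists it as a common side effect and a reactivation risk. What is at stake is mainly an avoidable exposure to a live vaccine under immunomodulation. Secondarily, treatment stopped before Week 16 would cost that patient's on-treatment primary assessment.

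**Working it through.** The plan gives no figure on this point to reproduce. The check is a comparison of texts, followed by simple arithmetic on deferral.

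**1. Side by side**

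| Place | Governs | Live vaccine on study | Zoster exception |
|---|---|---|---|
| 4.2 | Entry | Excluded if expected | Yes |
| 1.6 | Conduct on drug | Advised against | No |
| 3.3, Table 1 footnote | Conduct on drug | Stop treatment | No |
| 3.6 | Conduct on drug | Stop treatment | No |

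The protocol's other mentions of zoster concern infection or reactivation, not vaccination. Nothing reconciles the four entries.

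**2. What the exception does under each meaning**

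- *Non-live vaccine meant.* The exception is unnecessary, because the rule never covered such a product.
- *Live vaccine meant.* The patient is admitted. If the vaccine is given on drug, section 1.6 is disregarded and treatment must stop.

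The wording needs correcting under either meaning. The parenthesis may cover both parts of the criterion or only the on-study part; the on-study part is covered in both cases.

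**3. Can all four texts be obeyed together?** Yes. The site can defer the vaccine until drug has ended or use a non-live product.

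**4. Deferral if the criterion is tied to time on drug**

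- Core study: "Treatment will take place from Day 0 to Week 16" (section 5.2), so 16 − 0 = 16 weeks from Day 0.
- With "the option to enroll in a 3 month extension with a dose escalation to 4 mg" (section 3.3): 16 weeks + 3 months. Three months is taken as 12 weeks, because Table 3 lists drug through Week 24 and not at Week 28, and the visit list dispenses at Week 24 but not at Week 28. Result: 16 + 12 = about 28 weeks.

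**5. Deferral if the criterion keeps its present span, the whole study**

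- Core study: 16 weeks of treatment + 4 weeks of follow-up = about Week 20.
- With the extension: the last visit in Table 3, about Week 32.

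The whole-study wording therefore adds 20 − 16 = 4 weeks, or 32 − 28 = 4 weeks, during which the patient is already off drug.

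**6. Scale of one affected patient.** Section 3.2 states "12 subjects will be enrolled in this study". One patient is 1/12 = 8.3% of the sample. This is not an estimate of impact, since the number affected is unknown.

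**The case against.** The strongest reply is that nothing here conflicts. Section 4.2 decides who may enter; the other three places decide what happens on drug. Admitting a patient is not permission to vaccinate on drug, section 1.6 remains as a preventive instruction, and the type of zoster vaccine is never named, so the parenthesis may only be meant to reassure sites that zoster vaccination is acceptable. The exception can also operate harmlessly: the study includes a 4-week follow-up after treatment, when a live vaccine would be on study but not concurrent with drug, and no treatment would be left to stop.

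Much of this stands, and it rules out three readings that a reader might infer.

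- *Section 4.2 authorises live zoster vaccination on drug.* It does not; it only declines to exclude such a patient, and the stop rule still applies.
- *Sites cannot comply with all the texts.* They can, as shown above.
- *The primary result is biased by a calculable amount.* The documents give no count of affected patients. The stop rule ends treatment, not participation. Section 4.4.1 provides for continued follow-up after withdrawal, and section 7.3 keeps every dosed patient in the analysis.

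What the reply does not remove is the mismatch itself. As written, the exception has effect only for a live product and is not confined to off-drug periods. With additional exclusions barred, the site has no stated vaccine-based ground for declining a patient who plans a live zoster vaccine during treatment.

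**Conclusion.** The point holds as a minor safety inconsistency. The entry screen is removed for a vaccine that the conduct rules treat as incompatible with drug. This rests on a literal reading of the parenthesis as an exception to a live-vaccine rule; the sponsor may have had a non-live product in mind, and the wording should then say so.

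The number of patients affected is unknown and may be zero, so no effect on the estimate can be given. For any patient whose treatment stopped before Week 16 for this reason, the loss is the on-treatment value of the primary assessment, not necessarily the patient's follow-up.

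**What to change.** Split the section 4.2 criterion into two separate parts.

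- **(a) Before entry.** Keep the 12-week look-back unchanged, with whatever zoster exception the sponsor intends for it. The split matters: replacing the single closing parenthesis could remove a pre-entry zoster exemption if it was meant to cover both parts.
- **(b) On study.** Exclude a patient for whom a live vaccine, live herpes zoster vaccine included, is planned or foreseen during the time on study drug, and state that a non-live herpes zoster vaccine is allowed.

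Sections 1.6, 3.3 and 3.6 need no change. The cost is a short wording amendment. The downside falls on a patient who plans a live zoster vaccine: that patient must use a non-live product or defer for at least 16 weeks from Day 0, or about 28 weeks with the extension. If part (b) keeps the whole study as its span, deferral runs to about Week 20, or Week 32 with the extension. Tying it to time on drug avoids those extra 4 weeks and matches section 1.6.

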4.3 Subject Recruitment, Enrollment and Screening

- From the Principal Investigator or Co-Investigator clinical practices
- Screening requirements or qualifying lab values
- Evaluation and documentation of inclusion/exclusion criteria

4.4 Early Withdrawal of Subjects

4.4.1 When and How to Withdraw Subjects

- Subject safety issues
- Failure of subject to adhere to protocol requirements
- Disease progression
- Subject decision to withdraw from the study (withdrawal of consent)

Subjects who withdraw from the study for any reason will have their information recorded at the time of withdrawal. At the time of withdrawal, the subject will be considered at the final treatment date and will move into the treatment observation phase (4 weeks). Subjects will not be replaced. Follow up for subjects will continue to follow the normal follow up (Table-2)

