Individuals will then initiate treatment for all lesions of LP once daily and will be evaluated weekly and assessed by PGA of skin, oral mucosa, and hair, BSA, lesion count, Modified CAILS, Pruritus VRS, VAS and NRS scales, Skindex-16, and LPQOL between weeks 0-16 (see Appendix). Week 16 will be the primary endpoint. Therapy will be stopped and the individuals will be evaluated at week 20 after an observation period of 4 weeks and assessed by PGA, BSA, lesion count, mCAILS, Pruritus VRS, VAS and NRS scales, Skindex-16, and LPQOL. Laboratory and safety monitoring will occur at weeks 1, 2, 3, 4, 8, 12, 16, 20, 24, 28, and 32. 3D Photographs will be taken at weeks 0, 1, 2, 3, 4, 8, 12, 16, 20, 24, 28, and 32. Individual lesions will be circled at each visit and the exact area of each lesion will be measured. Up close photos will be taken of the disease.

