STELARA	Ustekinumab	16 weeks
TALTZ	Ixekizumab	10 weeks
TREMFYA	Guselkumab	12 weeks
XOLAIR	Omalizumab	16 weeks

Table-3: Screening and Visits (+/- 3-day window)

	Screening	Day 0	Week 1	Week 2	Week 3	Week 4	Week 8	Week 12	Week 16	Week 20	Week 24	Week 28	Week 32
Baricitinib (LY3009104)		Х	Х	х	х	Х	Х	Х	Х	Х	Х		
Physical Exam	Х	Х	Х	Х	Х	Х	Х	Х	Х	Х	Х	Х	Х
Adverse Event Assessment		Х	Х	Х	Х	Х	Х	Х	Х	Х	Х	Х	Х
Chest X-ray	Х												
Assessments: PGA, BSA, lesion number, mCAILS, Skindex-16, Pruritus VAS, VRS & NRS, LPQOL		х	х	х	х	х	х	х	х	х	Х	Х	Х
Photographer		Х	х	Х	Х	x	x	x	х	X	Х	Х	Х
Skin Biopsy (tissue/serum bank)		Х		Х									
ECG	Х					Х							
Urine Pregnancy Test	Х	Х				Х	Х	Х	Х	Х	Х	Х	Х
Venipuncture	Х	Х	Х	Х	Х	Х	Х	Х	Х	Х	Х	Х	Х
Biomarker/RNAseq blood (tissue/serum bank)		Х	х	Х	x	х	х	х	х	х	Х	Х	Х
CMP	Х		Х	Х	Х	Х	Х	Х	Х	Х	Х	Х	Х
Lipid Panel	Х		Х	Х	Х	Х	Х	Х	Х	Х	Х	Х	Х
СРК	Х		Х	Х	Х	Х	Х	Х	Х	Х	Х	Х	Х
CBC	Х		Х	Х	Х	Х	Х	Х	Х	Х	Х	Х	Х
Quantiferon Gold	Х												
Hepatitis B	Х												
Hepatitis C	Х												

HIV	Х						
Coccidioidomycosis	Х						

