4.4.2 Data Collection and Follow-up for Withdrawn Subjects

At the time of withdrawal, the reason for withdrawal will be recorded in the CRF. Individuals who withdraw will go into the observation phase for 4 weeks. If a subject withdraws consent, attempts will be made to obtain permissions to collect follow up information.

5 Study Drug

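### Section 4.4 gives two follow-up statements for withdrawn subjects; if the 4-week one is followed, anyone withdrawn before Week 12 has no Week 16 PGA, the primary endpoint

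*Combined protocol and SAP*

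**What the plan says.** Section 4.4.1 lists safety issues, non-adherence, disease progression and the subject's own decision as reasons for withdrawal. It then says that "the subject will be considered at the final treatment date and will move into the treatment observation phase (4 weeks"), that nobody is replaced, and finally: "Follow up for subjects will continue to follow the normal follow up (Table-2"). Section 4.4.2 repeats the shorter period: "Individuals who withdraw will go into the observation phase for 4 weeks".

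The table cited is headed "Table 2: Washout Periods for Monoclonal Antibodies (Biologic Drugs"). The visits are in "Table-3: Screening and Visits (+/- 3-day window").

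The primary endpoint in Section 3.4 is "Overall response by PGA of skin at week 16". For subjects who complete treatment, Section 3.3 describes a "treatment epoch (16 weeks from screen/washout), and follow up epoch (4 weeks"), and Section 3.1 says: "Therapy will be stopped and the individuals will be evaluated at week 20 after an observation period of 4 weeks".

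Section 7.3 considers for analysis everyone who took at least one dose. Section 7.2 offers a mixed model if data are missing at random, with last observation carried forward as a sensitivity analysis. Both are described for change in the lesion over time.

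**The concern.** A site reading Section 4.4 cannot tell whether a subject who withdraws at, say, Week 4 is seen for 4 more weeks and then released, or keeps attending through Week 16. The answer decides whether the primary endpoint exists for that subject.

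The subjects affected are not a random subset. Progression and safety are named withdrawal reasons, and progressive disease is Grade 6, the worst grade of the PGA scale in the Appendix. Under the 4-week statement, Week 16 values would go missing mainly among subjects doing badly.

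These subjects still belong to the Section 7.3 population, but no section says how they are classified on Week 16 PGA response. The missing-data methods in Section 7.2 are not tied to that response, and a Week 16 PGA that was never taken cannot be obtained later. Sections 7.1 and 7.2 give the trial's purpose as producing estimates for planning future studies, so a response rate with an unclear denominator weakens its main product.

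**Working it through.** The plan gives no dropout rate or missing-data allowance, so there is no figure of its own to reproduce. Section 7.2 sets the 12 subjects on logistical and financial grounds.

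**Inputs.** Primary assessment at Week 16 (3.4). Observation after withdrawal, 4 weeks (4.4.1, 4.4.2). Visit window of 3 days either side (Table-3). 12 subjects (3.2), not replaced (4.4.1).

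**Step 1: which withdrawals lose Week 16.** Under the 4-week statement, follow-up ends at withdrawal week + 4.

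- Week 4: 4 + 4 = 8, not reached.
- Week 8: 8 + 4 = 12, not reached.
- Week 11: 11 + 4 = 15, not reached.
- Week 12: 12 + 4 = 16, just reached.

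The cut-off is 16 − 4 = Week 12. Using the early edge of the window it is 16 − 3/7 − 4 ≈ Week 11.6, which changes nothing of substance. For withdrawal from Week 12 up to Week 16 the observation phase spans Week 16, so an off-drug Week 16 visit is possible.

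**Step 2: the readings of normal follow-up.**

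- *The full visit schedule.* Section 3.6, Section 8.1 and Supplemental 3 also write Table-2 where the visit or laboratory schedule is meant, so Table-3 is probably intended here. The Week 16 visit is then kept, and the sentence conflicts with the 4-week statement.
- *The standard 4-week period after treatment* (3.1, 3.3). The conflict then largely disappears, but the Week 16 gap for withdrawals before Week 12 becomes certain.

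Both readings leave something to correct.

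**Step 3: effect on the response rate.** One subject is 1/12 = 8.3 percentage points. As an illustration, take 2 subjects without a Week 16 PGA and 5 responders among the other 10 (exact 95% intervals):

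- both counted as non-responders: 5/12 = 42% (15% to 72%);
- assessed subjects only: 5/10 = 50% (19% to 81%);
- both counted as responders: 7/12 = 58% (28% to 85%).

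**Step 4: how many subjects.** This rests on an assumption: 5% to 20% withdraw before Week 12.

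- Expected number: 12 × 0.05 = 0.6 to 12 × 0.20 = 2.4.
- Chance of at least one: 1 − 0.95^12 = 46% to 1 − 0.80^12 = 93%.

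**Step 5: can the analysis section fill the gap?** The mixed model applies only if missingness is at random, which is doubtful when progression is a reason for leaving. Neither it nor the carried-forward analysis is specified for PGA response. Either could supply a value, but not an observed Week 16 assessment.

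**The case against.** The strongest reply is that the protocol never tells the site to skip Week 16. A reader might infer that it does, but the same paragraph says normal follow-up continues, and on the Table-3 reading every early stopper still has the visit. This stands: the loss depends on which sentence is followed.

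A reader might also infer that placing a withdrawn subject at the final treatment date means filing the withdrawal-visit value as Week 16 and the value 4 weeks later as Week 20. The wording leaves room for that, but no section assigns withdrawal data to those slots. It is a reason to clarify, not a planned practice.

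It is tempting to size the problem with the 3/37 adverse-event discontinuations at 2 mg in the Phase 2 atopic dermatitis study (Section 1.4). That count is from another disease and includes the washout, so it does not give a rate of stopping before Week 12 in lichen planus.

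A subject withdrawn for progression is also already known to be failing, since information is recorded at withdrawal, so the 58% bound is unlikely where progression is the reason. And drug interruption and discontinuation (Section 8.1) and consent withdrawal (Section 4.4.2) are each addressed in the protocol. Both points are fair. Yet nothing links those provisions to the efficacy visits, and nothing says how a subject withdrawn at any stage counts at Week 16.

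Finally, sampling error in 12 subjects is larger than the 42% to 58% spread. That lowers the priority, but does not make an avoidable and outcome-related gap acceptable.

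**Conclusion.** The point holds conditionally. Section 4.4 contains two follow-up statements that must be reconciled and a wrong table reference. If the 4-week statement governs, withdrawal before Week 12 removes the Week 16 PGA, for reasons that include poor outcome; if the Table-3 schedule governs, the PGA is kept. On either reading, the handling of early stoppers in the primary response is unstated.

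The size is 8.3 points per subject. The 42% to 58% range is an example, and the 0.6 to 2.4 expected subjects rest wholly on the assumed 5% to 20%. Because Section 7.2 limits the study to estimation, the consequence falls on the reported response rate and what is planned from it, not on power or type I error. It should be fixed, but it does not put the study as a whole in doubt.

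**What to change.** These changes concern data collection and analysis only; no treatment or stopping rule is proposed.

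1. Reconcile Sections 4.4.1 and 4.4.2 so that stopping study drug is distinguished from withdrawing consent.
2. For subjects who stop drug but still consent, keep the efficacy assessments, at minimum the Week 16 PGA of skin, at their original calendar weeks. Record the last-dose date and any new treatment for lichen planus.
3. State that a withdrawal-visit value is not filed as Week 16.
4. State in Section 7.2 how early stoppers, including those who start another treatment for lichen planus, count in the Week 16 PGA response among all dosed subjects. One option is to count them as non-responders, with the observed value as a sensitivity analysis.
5. Correct Table-2 to Table-3 in Section 4.4.1, and wherever else the visit schedule is meant.

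The cost is protocol wording and a few off-drug visits of a kind already designed. Subjects who withdraw consent may still be lost, and the rule in item 4 then covers them.
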